### **3 STUDY DESIGN**

The proposed study utilizes a single-group, uncontrolled design to assess the feasibility and acceptability of telephone-delivered mindfulness training designed to alleviate caregiver burden for rural caregivers of African American individuals with moderate to severe dementia. A care partner—the person who provides additional help—is included in the intervention. The primary outcome is feasibility of the telephone-delivered mindfulness intervention as assessed by an 85% retention rate with completion of at least 6 of the intervention sessions. Pre- and post-participation interviews will assess acceptability. A diagram of the intervention and assessment plan is provided in Figure 2.

**Figure 2. Intervention design\***

\*In-person assessments and retreat were changed in March 2020 due to COVID pandemic

**SPECIFIC AIM 1:** To determine the feasibility and acceptability of a telephone-delivered mindfulness training intervention (TMT) in decreasing caregiver burden among informal caregiving teams caring for African Americans with dementia.

The primary outcomes are feasibility and acceptability among primary caregivers and also among care partners.

**SPECIFIC AIM 2:** To explore, on a preliminary basis, the effects of the training on caregiver burden and relevant secondary outcomes for both caregiving team members. Secondary outcomes include the following:

1. Pre-post intervention differences in caregiver burden (Zarit Burden Interview);
2. Pre-post intervention differences in coping emotion regulation and coping styles (Cognitive Emotion Regulation Questionnaire);
3. Pre-post intervention differences in tolerance of uncertainty (Intolerance of Uncertainty Scale);
4. Pre-post intervention differences in anger, anxiety, and global self-perceived health (PROMIS short forms);
5. Pre-post intervention differences in family satisfaction (Family Satisfaction Scale), perceived social support among the caregivers (PROMIS Social Support short forms) and family conflict around caregiving (Family Conflict Scale);
6. Pre-post intervention differences in caregiver self-efficacy;
7. Pre-post intervention differences in mindfulness (CAMS-R scale), hopefulness, and optimism (Meaning and Purpose Scale).

**SPECIFIC AIM 3:** To explore comfort with and willingness to adopt technologies (e.g. telephone-based, web-based) to access mindfulness practices and existing caregiving educational resources.

1. In interviews with both the primary caregivers and the care partners, we will investigate comfort and experience with internet devices, including smartphones, tablets, and computers. For half of the intervention groups, we will ask these questions in post-participation interviews, including exploring how individuals are currently using or would like to use these technologies (e.g., voice activation, use of bookmarks).
2. For half of the intervention groups, we will ask questions about technology before the intervention and will offer each family a tablet loaded with intervention materials, including the contents of the participant binder. Post-participation interviews will include questions about the ease of use and perceived value of the tablets.

The study population will consist of 32 caregivers (CG) of African Americans care recipients (CR) with a cognitive or memory problem severe enough to prevent them from caring for themselves without assistance. Because African Americans with Alzheimer's disease and related dementias (ADRD) are less likely to have a formal diagnosis and because a formal diagnosis would not impact the potential value of the intervention for the caregiver, the study does not require a formal diagnosis. Instead, the study will require a level of disability as perceived by the caregiver to be at least moderate (see Inclusion Criteria). The study population also includes the 32 additional caregivers, care partners (CP) identified by the primary caregiver as informal team members who provide assistance. No control group is planned.

Additional participants in the study will include approximately 10 key informants from the community who will provide context, advice on cultural relevance, and advice on intervention language. These individuals may consist of informal caregivers, former caregivers, members of the Council on Aging, members of African American sororities affiliated with the Alzheimer's Association of Eastern North Carolina, or African American formal caregivers affiliated with hospitals in Eastern North Carolina.

Primary caregivers will come from Lenoir County, Wayne County, and surrounding counties in rural Eastern North Carolina. Caregiver assessments will take place in the home, or another location of the caregiver's choice. (During and following the COVID pandemic, this assessment will take place via telephone for all participants.) Care partners are not restricted geographically. Assessments of Care Partners will take place by telephone (or in a separate room in the home if they are present).

The research team will work with the individuals and organizations including the Alzheimer's Association of Eastern North Carolina (AAENC), the Study Physician, Research Fellows, and local pastors to develop a handbook of relevant caregiving resources for families (available both as a hard copy and, in half of the groups, electronically) as well as mindfulness exercises. Included in the handbook will be information about additional training for addressing CR behavioral problems (e.g., WeCare Advisor), training not covered explicitly by the proposed intervention.

The total duration of participation includes: 1) a pre-participation assessment up to 6 weeks prior to the intervention; 2) eight weeks of intervention calls plus retreat; and 3) a post-participation interview and assessment within four weeks of the last intervention call.

Interventions will take place over the telephone for the 8 mindfulness training sessions. The retreat, occurring between sessions 5 and 6, will take place either at a community location convenient to the majority of the group participants, or online via Zoom, during and after the COVID.. Please see Table 1 and the intervention handbook for details of the intervention.

**Table 1: Proposed curriculum for telephone-delivered mindfulness training**

Session	Topics	Caregiver/Care Partner Home Assignments
1	Introductions; what is mindfulness? Relevance to caregiving; Mindful relaxation breath and Mindfulness of sound	Practice mindful relaxation breath 3-5 minutes each day. Discuss your experiences with one another (CG-CP dyad).
2	Stress: How mindfulness can help us cope; Sitting meditation and mindful walking	Practice sitting meditation for 5 minutes once daily. Discuss your experiences with one another (CG-CP dyad).
3	Being and Doing Mind; Body scan and Mindful eating	Practice Body scan +/- mindful eating. Discuss your experiences with one another (CG-CP dyad).
4	Approaching Daily Life with Mindful Awareness; Breathing space/Mindful listening	Practice breathing space daily. Practice Mindful listening techniques in CG-CP dyad.
5	Mindfulness and Self-Care; instruction in self-compassion	Practice techniques learned. Continue to practice mindful listening in CG-CP dyad. Begin a self-compassion journal.
Retreat	Mindful communication: Listening, speaking, difficult conversations	(no homework but participants are encouraged to reflect upon the day and discuss with one another)
6	Mindfulness and Resilience; Compassion for the difficult person	Practice techniques learned. Practice mindful listening and speaking and explore compassion practice in CG-CP dyad.
7	Gratitude: Appreciating the Journey; learning to express our appreciation and gratitude to self and others	Practice techniques learned for 10 minutes twice daily. Practice mindful speaking and listening dyad, focusing on gratitude for others. Reflect on and discuss what techniques you found useful and may wish to continue.
8	Mindfulness and Meaning in Everyday Life—the Journey continues	

## **4 SELECTION AND ENROLLMENT OF PARTICIPANTS**

### **4.1 Inclusion and Exclusion Criteria**

Informal caregiving teams will be composed of a primary and secondary informal caregiver, as defined as:

*any relative, partner, friend or neighbor who has a significant personal relationship with, and provides a broad range of assistance for, an older person or an adult with a chronic or disabling condition [in this case, Alzheimer's Disease or a related dementia]. These individuals may be primary or secondary caregivers and live with, or separately from, the person receiving care. (Family Caregiver Alliance, [www.caregiver.org](http://www.caregiver.org))*

The primary caregiver (CG) are adults who must:

- Care for a family member with dementia who identifies as Black or African American
  - Defined: Care recipient must have a diagnosis of dementia (reported by caregiver) or have a score of at 2 or higher on the AD-8 or a score of 8 or higher on the Functional Activities Questionnaire (FAQ).
- Provide regular, daily care (at least 4 hours per day) for a family member who has dementia
- Have another adult care partner (CP) who is willing to participate; someone who shares caregiving or helps make decisions regarding the person with dementia or Alzheimer's disease (may be remote and family member or friend)
- Have a telephone and be willing to participate in weekly calls
- Live in rural areas in Eastern North Carolina.
  - Defined: Eastern is defined as east of Wake County NC; rural is defined as listed as rural within the website <https://www.ruralhealthinfo.org/am-i-rural>

The primary caregiver is excluded if they:

- Are receiving active treatment for cancer
- Have been hospitalized 3 or more times in the last year

The care partner is eligible if they are 18 or older, have a telephone and are willing to attend weekly sessions. Care partners do not need to be living in the same geographic region as the primary caregiver.

## 4.2 Study Enrollment Procedures

**Community involvement.** Because little research has investigated dementia caregiver needs in eastern NC, our team proposes adjunctive qualitative methods. To assist in adapting the mindfulness-training intervention components and the handbook, we plan to conduct key informant interviews. Key informants will include local pastors, members of African American sororities affiliated with the AAENC, and members of the local Council on Aging. Additionally, we will plan interviews with African American caregivers of people with dementia

**Advisory Council.** We will also recruit an Advisory Council of 5-8 individuals. We will share the results of feasibility data and qualitative analyses with the Advisory Council and utilize their input in refining improving the intervention. The Advisory Council may also review the intervention manual and study logistics and provide recommendations.

**Recruitment, screening and consent.** We plan to recruit participants in conjunction with local service providers and community organizations in Eastern NC Counties, including AAENC and local pastors. These counties are chosen for their high AA populations (>30%) and existing relationships with UNC researchers. Should recruitment from these counties be insufficient, we will extend the intervention to neighboring rural Eastern NC counties (e.g., Duplin, Sampson).

Recruitment partners (AAAENC, affiliated sororities, pastors, Council on Aging) will advertise the study to their membership. We will have a study website where potentially interested people can indicate interest. We will also provide study flyers to the UNC Hospitals clinics in Eastern NC counties and participate in local fairs and church-sponsored events in the counties. Once COVID pandemic occurred, we also relied on Facebook ads, radio/newspaper ads, NC Brain Registry and Duke family Caregiver Support e-news, and ‘snowballing’ (referrals from past participants). Interested individuals may contact the study directly or may provide permission to recruitment partners for the study staff to contact them. Recruitment partners may forward contact information to study staff.

After we identify individuals, we will provide details of the intervention and screen CGs over the telephone and pre-screen individuals with a telephone consent. We will visit CGs who meet the eligibility criteria in their homes to obtain a formal written consent for participation and to administer the baseline measures. (During COVID, these procedures will be conducted completely over the phone, with verbal consent process and phone assessments. In addition, staff will obtain a verbal consent addendum to allow unencrypted texting and emailing for the main purpose of study activities reminders.) At that time, we will provide a binder with local and downloaded caregiver resources as well as mindfulness activity instructions. Participants may also access audio files with recorded mindfulness activities. In the second half of the program, participants will receive a tablet loaded with all of the contents of the binder as well as bookmarked links to ADRD information sites.

The primary caregiver will be asked to invite a care partner to participate in the study and will obtain that person’s permission for us to contact them. Once permission is confirmed with the caregiver, study staff will contact the potential care partner, describe the study, and obtain verbal consent to proceed with assessments (and unencrypted messaging) as well as an invitation to participate in the intervention.

## **5 STUDY INTERVENTIONS**

### **5.1 Interventions, Administration, and Duration**

The study intervention is the mindfulness training for caregivers and care partners. The mindfulness training is offered in 8 weekly telephone sessions plus one weekend retreat. Respite care for the care recipient is provided for the retreat if needed.

### **5.2 Handling of Study Interventions**

Each participant will receive a resources handbook (binder) containing the following:

- Descriptions of each class section and suggested homework exercises;
- Detailed descriptions of mindfulness practices taught in the class;
- Instructions for how to access recorded mindfulness practices;
- A list of community resources for individuals with ADRD and their caregivers, including contact information;
- A list of national resources for individuals with ADRD and their caregivers;
- Instructions for caregivers based on material published by the researchers ([name], [name]);
- Select downloaded materials from the Alzheimer's Association of Eastern NC and other relevant websites.

Half of the groups will receive an electronic tablet loaded with the handbook, recordings, and links to resources bookmarked. We will program voice-enabled personal assistants on the tablet to enable access to bookmarked resources. We will investigate the best way to provide internet service for each participating family for at least 4 months (e.g., cell, DSL, cable). During the baseline (in-home) visit, we will teach CGs how to use the handbook. CGs who receive the tablet will also learn how to use it in the baseline visit. In follow-up interviews, we will ask to what extent CGs used the handbook, tablet (if relevant), and call-in lines. Given it is unclear if and how technologies will be used in this population, this aspect of the study will provide insight on which components of the intervention will be most useful to include in future iterations. Because half of the groups will receive the tablets, we will be able to examine the difference in adherence and engagement between groups with the tablets and without the tablets.

For the intervention, each trained, experienced mindfulness instructor will work from an instructor's manual prepared by [name]. The instructor's manual, designed for experienced mindfulness instructors, will detail the intervention components, providing tips on teaching the material and responding to participant questions. Consultant [name], an expert in telephone-delivered mindfulness, will review and edit the instructor's manual.

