As part of intervention planning, using interviews, we will investigate comfort with a smartphone/tablet. We will implement the tablets among half of the intervention groups so that we can compare acceptance between groups with and without the technology.

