## 7.4 Reporting Procedures

All reported events will be reported to the Safety Monitoring Committee and IRB for review twice a year (after the second, fourth, sixth, and eighth groups) and annually, respectively. SAEs will be reported to the Safety Monitoring Committee and IRB within 24 hours of the study staff receiving the report from a participant.

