The SMC will meet in person (or virtually for long-distance members as needed) at least 4 times throughout the study to review the Data and Safety Monitoring Report: 1) prior to first enrollment; 2) after the first 2 cohorts (2 8-week sessions); 3) after 6 cohorts have completed (6 8-week sessions); 4) at study completion (8 8-week sessions).

Additional meetings (ad-hoc) will occur as requested by the PI for review of unexpected adverse events or any SAEs that occur. Any recommended changes by the SMC will be submitted to the UNC IRB for approval.

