Hypothesis 5: Compared with baseline levels, we hypothesize that training in mindful communication reduce family conflict around caregiving (Family Conflict Scale).

Hypothesis 6: Compared with baseline levels, we hypothesize that mindfulness training will reduce anger and anxiety (PROMIS scales).

Hypothesis 7: Compared with baseline levels, we hypothesize that mindfulness training increase global self-perceived physical health (PROMIS short forms).

Hypothesis 8: Compared with baseline levels, we hypothesize that mindfulness training increase meaning and purpose (PROMIS short form).

Hypothesis 9: Compared with baseline levels, we hypothesize that mindfulness training along with a caregiver resources handbook will increase caregiver general and emotional self-efficacy (PROMIS scales).

Hypothesis 10: Compared with baseline levels, we hypothesize that mindfulness training will increase family satisfaction (Family Satisfaction Scale).

Hypothesis 11: Compared with baseline levels, we hypothesize that mindfulness training will increase mindfulness (Cognitive and Affective Mindfulness Scale).

SPECIFIC AIM 3: To explore comfort with and willingness to adopt technologies (e.g. telephone-based, web-based) to access mindfulness practices and existing caregiving educational resources. As part of intervention planning, using interviews, we will investigate comfort with a smartphone/tablet. For half of the groups of participants, we will provide a tablet loaded with the handbook and all of the intervention materials. In this way we can compare engagement and program acceptability rates between groups who received the tablets and those who did not.

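### Does the exploratory tablet comparison need a written limit on attribution, given that tablets appear to go to the later groups?

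*Combined protocol and SAP*

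**What the plan says.** Three sections announce the comparison. Section 1.2: "We will implement the tablets among half of the intervention groups so that we can compare acceptance between groups with and without the technology". Section 5.2: "Because half of the groups will receive the tablets, we will be able to examine the difference in adherence and engagement between groups" with and without tablets. Section 9.1: "we can compare engagement and program acceptability rates between groups who received the tablets and those who did not".

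Only section 4.2 indicates which groups get them: "In the second half of the program, participants will receive a tablet loaded with all of the contents of the binder". Section 5.2 adds: "CGs who receive the tablet will also learn how to use it in the baseline visit". Section 7.4 counts the groups in sequence, with reports "after the second, fourth, sixth, and eighth groups", and section 7.6 also ends the study at eight cohorts. Section 9.2.1 states that randomization does not apply.

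Section 9.4.3 lists the technology outcome as qualitative. Section 9.5 gives no method for the tablet contrast. Its promise of caution belongs to the sentence on unadjusted multiple comparisons of the questionnaire measures.

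**The concern.** If the tablet groups are the last four of eight, no tablet group runs alongside a non-tablet group. Whatever differs between early and late groups is carried into the contrast. The protocol describes several things that could differ: recruitment channels added during the pandemic and message reminders (section 4.2), an online retreat (section 3), and changes to the intervention that instructors may suggest after participant feedback (section 10.2).

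Section 5.2 also says that "this aspect of the study will provide insight on which components of the intervention will be most useful to include in future iterations". If that judgement rested on the between-group difference, better attendance in later groups could be credited to the tablet and carried into the next trial. No section warns against that reading.

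A related worry is interview timing. Section 3 asks technology questions before the course in the tablet half and after it in the other half, while section 6.1.2 puts comfort with technology in the caregiver's baseline interview.

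**Working it through.** **1. The plan's own precision figure.** Section 9.2 gives 85% with n = 32 as 72.5 to 97.5. The simple (Wald) interval is 0.85 ± 1.96 × √(0.85 × 0.15 / 32) = 0.85 ± 0.124, or 72.6 to 97.4. It reproduces within about 0.1 point. The documents give no such figure for the tablet contrast.

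**2. Is tablet status tied to order?** Section 4.2 alone could mean the later weeks of each course. Section 5.2 rules that out, because half of the groups receive tablets and their caregivers are taught to use them at baseline. No section describes a random or balanced choice. Tablets in groups 5 to 8 is therefore the consistent reading, though it is an inference.

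**3. What order could do.** The mean position is 6.5 for groups 5–8 and 2.5 for groups 1–4, a gap of 4.
- A linear drift of d points per group appears as 4d. For assumed d = 1, 2 or 3 that is 4, 8 or 12 points.
- A single step s after group k = 0, 1, …, 8 appears as 0, 0.25, 0.50, 0.75, 1.00, 0.75, 0.50, 0.25, 0 times s.

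The documents give neither d nor s, and no group start dates. A change made before group 1 contributes nothing. These formulas show that bias is possible; they do not estimate it.

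**4. What the contrast can resolve.** Inputs: 32 dyads, 28 expected to complete (section 9.2); up to four dyads per group (section 2.2); 85% assumed in each half. Half-width = 1.96 × √(2 × 0.85 × 0.15 / n), with n per half. Design effect = 1 + (m − 1) × ICC, with m = 8 participants or 4 caregivers per group and ICC assumed at 0.05 to 0.10.

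| Comparison | Half-width, points | With clustering, points |
|---|---|---|
| 32 v 32 participants | 17.5 | 20.3 to 22.8 (design effect 1.35 to 1.70) |
| 16 v 16 caregivers | 24.7 | 26.5 to 28.2 (design effect 1.15 to 1.30) |
| 28 v 28 completers, both roles | 18.7 | not computed |
| 14 v 14 completers, one role | 26.5 | not computed |

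**5. Would a balanced order help?** Tablets in groups 2, 3, 6 and 7 give a mean position of (2 + 3 + 6 + 7)/4 = 4.5, against (1 + 4 + 5 + 8)/4 = 4.5 for the rest. Linear drift cancels, but n per half is the same, so every half-width above stands.

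**6. What the statement about future iterations refers to.** In section 5.2 the order is: follow-up interviews ask how far caregivers used the handbook, tablet and call-in lines; then comes the statement on components, explained by uncertainty about whether and how technology will be used; only then comes the group comparison. The natural reference is reported use.

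**7. Interview timing.** Section 6.1.2 already gives caregivers a common baseline question on comfort with technology; section 3 can be read as adding detail on devices and use. The announced comparisons concern acceptance, adherence, engagement and program acceptability. The adherence section measures acceptance by attendance at six or more sessions. None is stated to use the comfort-with-technology answers.

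**The case for a change.** The strongest case for a change is that the gap is real and cheap to close. Sections 1.2 and 9.1 give comparison as the reason for equipping half of the groups, and section 9.1 speaks of rates, so the qualitative label in section 9.4.3 does not cover everything. Feedback-driven changes under section 10.2 could make later groups differ whatever the timing of the pandemic changes. A few sentences would tell readers not to attribute a difference to the tablet.

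What stands is the fact: tablet status follows group order on the best reading, and no section says so. What does not stand is that the plan goes wrong as a result. Comparing and examining are descriptive commitments, and the missing sentence would guard against an inference that the plan never draws. An analyst reporting an unrandomized early-versus-late contrast in a one-arm pilot would show it by cohort and state that limit.

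Reordering the tablets is a trade-off. Section 3 asks the non-tablet groups how they would like to use the technologies. Starting tablets early would give up the chance for those answers to shape the tablet content, and would require devices and internet service sooner. The contrast would remain descriptive.

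**Conclusion.** The observation is correct, but no change to the plan follows. The tablet contrast is probably aligned with group order, so a difference can be described but not credited to the tablet. The plan claims no more than description. With half-widths of about 17 to 28 points, balancing the order would not make the contrast more than descriptive. Users' own accounts of tablet use, ease and value remain sound evidence for Aim 3, and the primary outcomes, sample size and error rates are untouched.

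This rests on reading section 4.2 as later groups, an even split of the dyads, 85% in each half and an ICC of 0.05 to 0.10. The last two are assumptions. The size of any time effect is unknown.
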